4.5 PHARMACOKINETIC AND PHARMACODYNAMIC ANALYSES

Not applicable for this study.

4.6 SAFETY ANALYSES

The safety analyses will be conducted on the Safety Population.

4.6.1 Exposure of Study Medication

Data of atezolizumab administration will be summarized using descriptive statistics and frequency tables, respectively, based on the Safety Population, considering all exposure data until the date of last study treatment, as reported for treatment phase on the Study Completion/Early Discontinuation page of the electronic case report form (eCRF).

The duration of treatment will be calculated in units of days as the difference of the start date of treatment until the date of the most recent study treatment at data cut-off plus 1, converted into months as described in section 4.

A treatment cycle is defined as 3 weeks (+/- 3 days) in duration. An atezolizumab treatment cycle will be counted as such if the first atezolizumab administration is given for this cycle.

The relative dose intensity of atezolizumab will be calculated as the total dose administered between the first and the last administration of study treatment divided by the amount of planned dose for this period multiplied by 100.

The total dose will be calculated as the sum of all doses that were administered during the time interval between the first and the last administration of study treatment, as entered on the eCRF.

The planned dose will be calculated as the amount of drug which should have been received during the time interval between the first and the last administration of study treatment based on a dose level of 1200 mg every 3 weeks, accounting for the theoretical duration of the last cycle. Consequently, the calculation of the planned dose will be performed as follows:

$$\text{Planned dose [mg]} = \frac{(last\ dose\ date - first\ dose\ date + 21) \times 1200}{21}$$

Time on treatment will be presented in two ways. First, for the purposes of describing the exposure to atezolizumab at the time of analysis, it will be presented in standard summary form without taking account of censoring. Second, for the purposes of estimating the time spent on treatment phase by the end of the study, it will be analyzed using the Kaplan-Meier method. A patient with a recorded end of treatment phase before or on the cut-off date will be considered as having experienced an end of treatment event on the date of last dose. Patients with ongoing treatment at the cut-off date will be censored at the time of last dose before or on cut-off date.

Duration of follow-up time will also be calculated using the reverse Kaplan-Meier method (that is, using the time variable for the Overall Survival (efficacy) analysis with the censoring flag reversed)

Atezolizumab exposure will be summarized as follows:

- Number of patients with infusion by cycle
- Descriptive statistics for time on treatment [months]
- Kaplan-Meier analysis of time on treatment and corresponding Kaplan-Meier plot
- Number of treatment cycles per patient during study
- Descriptive statistics for relative dose intensity
- Frequency table of treatment cycles by dose (categorized in original, below and above dose [dose = 1200mg, dose < 1200mg, dose > 1200mg])
- Number of patients with injection/infusion modified, overall and by reason for modification.
- Number of patients with dose modification, overall and by reason for modification

A by-patient listing of exposure data including site, patient identifier will be provided based on the Safety Population.

Additionally, for responders, the number of subjects treated after response by the number of cycles of treatment after response and the number of subjects still ongoing treatment at cutoff date will be presented. For progressors, the number of subjects treated after progression by the number of cycles of treatment after progression and the number of subjects still ongoing treatment at cutoff date will be presented. This will be based on the ITT population.

4.6.2 Adverse Events

Verbatim descriptions of AEs will be mapped to latest version of MedDRA thesaurus terms and graded according to the National Cancer Institute Common Terminology Criteria version 4.0 (NCI CTCAE v4.0).

Multiple occurrences of the same event will be counted once at the maximum severity.

The following AEs will be initially considered as AEs of special interest:

- Pneumonitis
- Colitis
- Endocrinopathies: diabetes mellitus, pancreatitis, adrenal Insufficiency, hypothyroidism/hyperthyroidism and hypophysitis
- Hepatitis
- Transaminitis Grade ≥ 2 (Aspartate aminotransferase (AST) or alanine aminotransferase (ALT) $>3x$ ULN and bilirubin $>2x$ ULN) OR AST/ALT $>10x$ ULN
- Systemic lupus erythematosus
- Neurological: Guillain-Barre Syndrome, myasthenic syndrome or myasthenia gravis, meningoencephalitis
- Nephritis
- Ocular toxicities (e.g., uveitis, retinitis, optic neuritis)
- Myositis
- Myopathies, including rhabdomyolysis
- Vasculitis
- Events suggestive of hypersensitivity, [infusion-related reactions](#), cytokine release, HLH and MAS
- Cases of potential drug-induced liver injury that include an elevated ALT or AST in combination with either an elevated bilirubin or clinical jaundice, as defined by Hy's law (see Section 5.3.5.7 of the protocol)
- Suspected transmission of an infectious agent by the study drug, as defined below:
Any organism, virus, or infectious particle (e.g., prion protein transmitting transmissible spongiform encephalopathy), pathogenic or non-pathogenic, is considered an infectious agent. A transmission of an infectious agent may be suspected from clinical symptoms or laboratory findings that indicate an infection in a patient exposed to a medicinal product. This term applies only when a contamination of the study drug is suspected.
- Cardiac toxicities of Grade ≥ 2 (e.g., atrial fibrillation, myocarditis, pericarditis)
- Autoimmune flare of Grade ≥ 3

Beside the listed AEs of special interest, Roche will provide a list of MedDRA Preferred Terms (basket) during the study to identify the AEs of special interest for the statistical analysis.

Treatment-emergent AEs (TEAEs) will be defined as any AEs with an onset date after the start date and time of first administration of study treatment and up to 30 days after

the date of last administration of study treatment (For SAEs and AEs of special interest up to 90 days).

AEs with onset on first dosing date, not recorded as starting before study treatment administration will be considered as TEAEs. Similarly, AEs with onset date prior first dosing date but worsening/change recorded on or after first dosing date will be considered as TEAEs.

Only TEAEs will be included in summary tables. AEs which are not treatment-emergent will only be included in the AE listings.

Patient rates for AEs will be presented and accompanied by the respective two-sided 95% Pearson-Clopper CIs.

In any AE summary tables, number and percentage of patients reporting at least one AE will be provided. In AE summary tables by SOC and PT, the number of reported events will be presented additionally.

Every occurrence of an AE in any patient will be counted in the total number of events.

In tables presenting frequency of AEs by worst grade, only the event with the highest grade will be counted when there are multiple occurrences of a same AE in one patient.

A missing NCI CTCAE grade will be imputed as follows: for a fatal AE, as Grade 5; for a non-fatal AE, as Grade 4.

A summary table will be provided presenting:

- Number and percentage of patients with any TEAE
- Number and percentage of patients with any Serious TEAE
- Number and percentage of patients with any related TEAE
- Number and percentage of patients with any related Serious TEAE
- Number and percentage of patients with any TEAE leading to study drug discontinuation
- Number and percentage of patients with any grade 3 to 4 TEAE
- Number and percentage of patients with any grade 5 TEAE
- Number and percentage of patients with any AESI
- Number and percentage of patients with any grade 3 to 5 AESI
- Number and percentage of deaths, overall and by reason
- Number and percentage of deaths on study treatment (i.e. within 30 days post last study treatment administration), overall and by reason

Following safety data will be summarized:

- TEAEs by SOC, PT and by worst grade
- TEAEs of grade 3 to 5, by PT and by worst grade
- TEAEs of grade 5, by PT
- TEAEs leading to study drug discontinuation, by SOC and PT
- TEAEs leading to study discontinuation, by SOC and PT
- TEAEs related to study drug, by SOC, PT and worst grade
- Serious TEAEs by SOC, PT and worst grade
- Serious TEAEs related to study drug, by SOC and PT
- AEs of special interest by category, PT and worst grade (with additional column for AESI of grade ≥ 3)

Death cases will be summarized as follows:

- Number of death events, overall and by primary cause of deaths, occurrence of an autopsy, number of death events within 30 days/ later than 30 days to 90 days and later than 90 days after first study treatment administration, number of death events within 30 days/ later than 30 days to 90 days and later than 90 days after last study treatment administration
- Number of death events by number of cycles started (1 cycle, 2 cycles, 3 cycles, 4 cycles, 5 cycles or more and broken down by number of days since last dose: ≤ 30 days, $>30 - \leq 90$ days or >90 days) and by primary cause of death and occurrence of an autopsy. A death event will be associated with the number of cycles the patient received, a cycle being counted when dose >0 . A summary table and the corresponding figure will be provided.

By-patient listings based on the safety population will be provided for the following types of AEs:

- TEAEs and AEs who do not meet the criteria of TEAEs
- AEs of special interest
- AEs leading to permanent treatment discontinuation
- SAEs
- Fatal AEs (i.e. grade 5 AEs)

In addition, a by-patient listing of death case will be provided based on the Safety Population. Deaths events will be categorized in days since first dose and days since last dose: ≤ 30 days, $>30 - \leq 90$ days or >90 days in this listing.

In the above listings, information relative to the following subgroups of interest will be included:

- ECOG Performance status: 0–1 vs. 2 (the category 2 includes patients who recorded status 2 at screening but 3 at baseline)

- Progression on, or within 12 months of, prior platinum-based treatment: yes vs. no
- Concomitant steroid treatment ongoing at baseline: yes vs. no
- History: non-urothelial or mixed urinary tract carcinoma histology vs urothelial
- AACI: ≤ 11 vs. > 11
- Renal impairment at study entry: yes vs. no
- Sex: female vs. male
- HIV status: negative vs. positive
- History of autoimmune disease: yes vs. no
- Presence of CNS metastases at baseline: yes vs. no
- Patients: < 65 years vs. ≥ 65 years
- Patients: < 70 years vs. ≥ 70 years
- Patients: < 75 years vs. ≥ 75 years
- Patients: < 80 years vs. ≥ 80 years
- Prior Lines of Treatment for Metastatic Disease: 0 vs 1 vs. 2 vs. 3
- PD-L1 expression: IC2/3 vs. IC0/1
- PD-L1 expression: IC0 to IC3
- IMvigor211-like patients: yes vs. no
- Regions: Australia/Canada/Western Europe vs Eastern Europe vs Other regions

In addition, the AE summary table described previously in this section will be repeated for each of the above subgroups.

A by-patient listing of immune-related thyroid disorders on the safety population will also be provided.

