- Participants were prohibited from having an autoimmune disease. Treatment of autoimmune diseases typically requires immunosuppressive therapies, the effects of which remain uncharacterized, vis-à-vis, atezolizumab immunotherapy. It is also imperfectly understood how checkpoint inhibition with atezolizumab may impact symptoms and progression of autoimmune diseases. For similar reasons, participants in prior studies were required to have disease that did not require treatment with systemic corticosteroids and/or other systemic immunosuppressive medications
- Participants were not allowed to have severely reduced kidney function (i.e., glomerular filtration rate  $\leq$  30 mL/min), a condition associated with poor health in general and a potentially increased risk of immune-mediated renal toxicity
- Participants were not allowed to be positive for HIV

Because cancer of the urinary tract is a heterogeneous disease (Kaufman et al. 2009), earlier atezolizumab studies were also restricted to relatively specific classes of patients, thereby limiting the number of additional factors that could complicate the final analyses. For example:

- Participants were only enrolled with advanced urothelial carcinoma. This restriction was easily tenable based on the fact that > 90% of bladder cancer cases have a urothelial histology (American Cancer Society 2016a), ensuring that the majority of clinical cases were being addressed in the trials
- Participants were required to have advanced on platinum-doublet therapy prior to entering the studies. This again made sense since platinum-doublet is standard first-line treatment of advanced UC (Bellmunt et al. 2014) and, thus, the majority of clinical cases should have been eligible for the study
- Finally, participants were prohibited from enrolling with CNS metastases, except in some highly defined situations if the metastases were asymptomatic. Although rare, CNS metastases in bladder cancer appear to be increasing in incidence and are associated with significant health burden and poor outcomes (Dhote et al. 1998; Protzel et al. 2002; Boyle et al. 2013; Chung et al. 2013). From both a safety perspective and a scientific perspective (e.g., the role of the blood-brain barrier in antibody drug delivery), inclusion of this class of patients in earlier atezolizumab trials was deemed premature

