Given the high unmet need for new therapies for advanced bladder cancer, it is of considerable interest to evaluate atezolizumab in a population of bladder cancer patients that mimics more closely a standard clinical population. As a first step in this process, the primary objective of Study MO29983 will be to analyze the safety of atezolizumab in a population of bladder cancer patients that includes patients who would have been screened out of many of the previous studies. The large majority of eligibility criteria in Study MO29983 remain unchanged from earlier trials and the safety of participants remains the highest priority. However, a small number of criteria have been broadened:

- Patients with a baseline ECOG performance status of 2 will now be eligible for enrollment, in addition to patients with ECOG performance statuses of 0 and 1
- CNS metastases will be allowed at baseline, if stable
- Patients with a renal clearance of  $\geq 15$  mL/min (rather than  $\geq 30$  mL/min) and/or a history of renal failure will be allowed in the study
- Prior treatment with non-platinum regimens will be allowed
- Patients with CNS metastases will be allowed to receive steroid treatments if the dose of prednisone is  $\leq 20$  mg/day (or equivalent)
- Patients with underlying controlled and stable autoimmune diseases will be allowed
- Patients with non-urothelial carcinoma of the urinary tract will be permitted to enroll in the trial

- Patients with HIV will be eligible, based on evidence suggesting that the PD-L1/PD-1 pathway may be operative in HIV infection and that PD-L1/PD-1 inhibition may have a role in reducing viral load

In addition to assessing safety, the current study will have secondary objectives to assess response and patient-reported outcomes, which will further advance the understanding of atezolizumab therapy in patients with cancer of the urinary tract. Finally, in exploratory analyses, the study will assess PD-L1 prevalence in tumor tissue using an IHC assay and will correlate a panel of biomarkers with efficacy and safety outcomes. These studies will continue to expand our understanding of atezolizumab and lay the groundwork for future clinical trials.

For additional rationale statements explaining the current study design, please refer to Section 3.3.

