#### ***Treatment Interruption***

Atezolizumab may be temporarily suspended in patients who experience toxicity considered to be related to study treatment. If atezolizumab is withheld for > 12 weeks, the patient will be discontinued from study drug. *Atezolizumab can be resumed after being withheld for >12 weeks if the patient is likely to derive clinical benefit. The decision to re-challenge patients with atezolizumab should be based on investigator's assessment of benefit-risk and documented by the investigator. The Medical Monitor is available to advise as needed. Atezolizumab treatment may be suspended for reasons other than toxicity (e.g., surgical procedures).* If a patient must be tapered off steroids

that have been used to treat adverse events, then atezolizumab may be withheld for more than 12 weeks from the last dose until the steroids are discontinued or reduced to a prednisone dose (or dose equivalent) of  $\leq 10$  mg/day. For patients with CNS metastases or autoimmune disease who require chronic steroid therapy, who have been receiving additional steroids to treat adverse events, and who now require a reduction in steroid dosage, atezolizumab may be withheld for more than 12 weeks from the last dose until the steroid dosage has returned to its baseline value. The investigator will determine the acceptable length of treatment interruption. The acceptable length of treatment interruption *must be based on an assessment of benefit–risk by the investigator and in alignment with the protocol requirements for the duration of treatment and documented by the investigator. The Medical Monitor is available to advise as needed.*

For the management of atezolizumab related adverse events please refer to [Appendix 11](#) and Section 6 of the latest version of the Investigator's Brochure.

For patients developing a new autoimmune disease not listed in [Appendix 11](#) and Section 6 of the latest version of the Atezolizumab Investigator's Brochure, or for patients with an autoimmune disease who develop a flare, the following dosing guidance should be applied:

- Grade 1 event: atezolizumab dosage should be maintained
- Grade 2 or 3 event: atezolizumab should be suspended until the subject responds to treatment of the autoimmune disease and the disease becomes stable (see rules above regarding maximum suspended time). The subject should be referred to an appropriate specialist

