#### **5.3.5.9 Preexisting Medical Conditions**

A preexisting medical condition is one that is present at the screening visit for this study. Such conditions should be recorded on the General Medical History and Baseline Conditions eCRF.

A preexisting medical condition should be recorded as an adverse event only if the frequency, severity, or character of the condition worsens during the study. When recording such events on the Adverse Event eCRF, it is important to convey the concept that the preexisting condition has changed by including applicable descriptors (e.g., "more frequent headaches," "flare," etc.).

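### SAP 4.6.2 plans no flare rate for patients with a history of autoimmune disease, and no table of AEs leading to treatment interruption

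*SAP*

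**What the plan says.** **Why these patients are in the study.** Protocol 1.4 explains why earlier trials excluded autoimmune disease: "It is also imperfectly understood how checkpoint inhibition with atezolizumab may impact symptoms and progression of autoimmune diseases". It then lists the broadened criteria, among them: "Patients with underlying controlled and stable autoimmune diseases will be allowed". Protocol 6.6 makes history of autoimmune disease a subgroup for key safety and/or efficacy parameters.

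**What a flare does to treatment.** For a flare of an existing autoimmune disease, protocol 5.1.2 maintains dosing at Grade 1 and stops it permanently at Grade 4. Between these: "Grade 2 or 3 event: atezolizumab should be suspended until the subject responds to treatment of the autoimmune disease and the disease becomes stable".

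**How a flare is recorded.** Protocol 5.3.5.9 sets no grade floor: "A preexisting medical condition should be recorded as an adverse event only if the frequency, severity, or character of the condition worsens during the study". Of the wording of the entry it says: "it is important to convey the concept that the preexisting condition has changed by including applicable descriptors"; flare is one of its examples. SAP 4.6.2 counts an event that began before the first dose and worsened on or after it as treatment-emergent.

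**How a flare is reported.** The list of AEs of special interest (AESIs) in SAP 4.6.2 follows protocol 5.2.3 and includes "Autoimmune flare of Grade" 3 or higher. AESIs are tabulated by category, preferred term and worst grade. For the subgroups, including autoimmune history, the SAP says: "In addition, the AE summary table described previously in this section will be repeated for each of the above subgroups".

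**Interruption.** Protocol 6.4 lists AEs that led to the drug being stopped or interrupted as one safety variable. SAP 4.6.2 has tables for stopping the drug and for leaving the study, and none for interruption.

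**The concern.** The study deliberately enrols patients whose existing disease might be made worse by the drug. A clinician will ask how many of them flared, how badly, and how many had treatment suspended for it. The one category that carries the name starts at Grade 3 and has the whole population as its denominator. The protocol's own suspension threshold is Grade 2. A Grade 2 flare that led to a suspension would therefore not be identifiable as a flare in any summary table, and the planned tables could not answer the question for the patients concerned.

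**Working it through.** **1. Trace of the planned outputs** (SAP 4.6.1 and 4.6.2)

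| Output | Grades of flare it can hold | Split by autoimmune history | Flare rate in that subgroup |
|---|---|---|---|
| AESI table, autoimmune-flare category | 3 and above | Not named | No |
| AESI table, categories with no grade floor (e.g. colitis, hepatitis, lupus, myositis, vasculitis) | All, for those diseases only | Not named | No; new disease and flares are mixed |
| TEAE table by system organ class, preferred term and worst grade | All | Not named | No; flares are spread over terms |
| Overview AE summary (any TEAE, serious, related, leading to drug discontinuation, Grade 3–4, Grade 5, any AESI, Grade 3–5 AESI, deaths) | All, unlabelled | Yes | No; no flare row |
| By-patient AE listings | All | Flagged | No; no count, percentage or interval |
| TEAEs leading to drug discontinuation | Flares that ended treatment | Only as a row of the overview | No |
| Infusion and dose modifications by reason (4.6.1) | Unclear whether withheld doses count | Not named | No |

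SAP 4.4.5 speaks of adverse-event and death tables in the plural by subgroup, but only for PD-L1 expression and its further breakdowns.

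**2. The plan's own interval method.** The exact limits are: lower = the 2.5% quantile of Beta(x, n − x + 1); upper = the 97.5% quantile of Beta(x + 1, n − x). For x = 5 and n = 1000 these give 0.16% and 1.16%, half-width 0.50%, as in SAP Table 1. All nine rows of that table reproduce.

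**3. Precision of the missing estimate.** The documents state neither the number of autoimmune patients nor a flare rate. Both are assumed here and varied (Grade 2 or above, 95% CI):

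| Patients with autoimmune history | 10% flare | 20% flare | 30% flare |
|---|---|---|---|
| 20 | 2 (1.2–31.7%) | 4 (5.7–43.7%) | 6 (11.9–54.3%) |
| 40 | 4 (2.8–23.7%) | 8 (9.1–35.6%) | 12 (16.6–46.5%) |
| 100 | 10 (4.9–17.6%) | 20 (12.7–29.2%) | 30 (21.2–40.0%) |

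**4. What the Grade 3 floor leaves out.** Take 8 of 40. If 25%, 50% or 75% of those flares are Grade 2, then 8 × 0.75 = 6, 8 × 0.50 = 4 or 8 × 0.25 = 2 are Grade 3 or above: 15%, 10% or 5% of 40. The gap depends entirely on the unknown grade mix. It also assumes that none of the Grade 2 flares falls in another AESI category.

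**5. What the denominator does.** SAP section 4 bases percentages on the whole analysis population. Take the middle case and suppose that all Grade 3 or higher flares occur in autoimmune patients. The AESI table would then show about 4/1000 = 0.4% (0.11% to 1.02%, as in SAP Table 1), whereas 4/40 = 10% (2.8% to 23.7%). Both are correct; only the second describes the patients at risk.

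**The case against.** Much of the opposing case stands.

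- **A reader might infer that the flare rate will be reported too low.** The documents do not support that. The category is labelled Grade 3 or higher and agrees with protocol 5.2.3, so its count is right for what it claims. No flare rate in autoimmune patients is planned that could be biased.
- **A reader might infer that the flare category is the only output containing flares.** It is the only one that bears the name. Many diseases in protocol Appendix 5 map to AESI categories with no grade floor, so a Grade 1–2 flare of, say, autoimmune hepatitis or lupus counts there and in the any-AESI row repeated by autoimmune history. Psoriasis, rheumatoid arthritis, Sjögren's syndrome and sarcoidosis have no category of their own. All grades reach the TEAE table and the flagged listings.
- **A reader might infer that flares which stop dosing are lost.** Flares that lead to permanent discontinuation are tabulated at any grade. What lacks a table is temporary suspension.
- **The preferred-term basket is not in the SAP.** The sponsor supplies it during the study, and whether it captures lower-grade flare terms cannot be settled from the documents.

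None of this produces a count and percentage of patients whose existing disease flared. A listing lets someone work that out afterwards, but it does not fix the definition in advance.

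**Conclusion.** The point holds as a gap in planned reporting. SAP 4.6.2 gives no flare rate, at any grade, for patients with autoimmune history, although the effect on such disease is part of the study's rationale and the subgroup is pre-specified. It also omits the interruption half of a safety variable that protocol 6.4 lists, which is where Grade 2 suspensions would show.

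No planned estimate is wrong, and the study is descriptive. The documents do not allow the gap to be sized; the figures for 20 to 100 patients and 10% to 30% flaring are assumptions that show only what precision the added table would have. At 20 to 40 patients the interval is wide, so the table would describe the risk and could not exclude a substantial one. This is a cheap improvement worth making before the final analysis.

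**What to change.** **Add to SAP 4.6.2:**

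1. For Safety Population patients with a history of autoimmune disease, the number and percentage, with Clopper-Pearson 95% CI, who have a treatment-emergent flare of the pre-existing disease: any grade, Grade 2 or above, and by worst grade. Split it by the baseline status already tabulated in SAP 4.3 (resolved, ongoing with treatment, ongoing without treatment).
2. The rule for identifying a flare: match the AE term to the disease recorded at baseline, with medical review of the resulting listing before database lock.
3. A table of TEAEs leading to interruption of atezolizumab, overall and by autoimmune history.
4. A footnote on the collection window. Serious events and events in AESI categories are collected to 90 days after the last dose, other non-serious flares to 30 days, and protocol 5.1 ends both earlier if new anti-cancer therapy starts. Lower-grade flares of different diseases are therefore not all followed for the same time.

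Leave the AESI definition and the clinical suspension rule unchanged.

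**Cost:** two tables and a medical review of a short listing. The flare table needs no new data, since worsening is already recorded as an AE and autoimmune history is already listed by patient.
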